**** Due to the recent safety signal, the study was fully unblinded to ensure the safety monitoring of the participants.***

Maternal participants 15 to 49 years of age (YOA) (inclusive, at the time of the study intervention administration) will be enrolled to receive either RSV maternal (RSV MAT) vaccine (120 µg of RSVPreF3) or the placebo control, between the 24^{0/7} to 36^{0/7} weeks of gestation (inclusive).

Approximately 378 eligible maternal participants will be enrolled* and randomized (2:1) to receive either RSV MAT vaccine or the placebo control. At least eighteen (5%) of the enrolled and randomized maternal participants will be between 15 and 17 YOA, inclusive. At the same time, infant participants (as yet unborn) will be further randomized (1:1:1) into sub-cohorts for blood sample collection for the assessment of immunogenicity at one of 3 timepoints (Day 43, Day 121 or Day 181 post-birth).

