 - Gestational diabetes, well-controlled on medications (with or without diet or exercise): i.e. when normoglycemia is maintained (fasting or preprandial blood glucose values <95 mg/dL [5.3 mmol/L], and/or postprandial blood glucose concentration <140 mg/dL [7.8 mmol/L] at 1 hour and/or postprandial blood glucose concentration: <120 mg/dL [6.7 mmol/L] at 2 hours).
 - Gestational hypertension, well-controlled on diet or medications below 160/110 mmHg.
 - Pre-eclampsia without severe features (i.e. eclampsia, severe hypertension [$>160/110$ mmHg], organ dysfunction, unstable or complicated by Hemolysis, Elevated Liver enzymes, and Low Platelets [HELLP] syndrome).
 - Fetal Growth Restriction in singleton pregnancies, with normal umbilical artery (UA) Doppler and estimated fetal weight 3 to 10th percentile for gestational age.
 - History of threatened preterm labor in the current pregnancy, with no cervical dilation greater than 2 cm or effacement exceeding 50%, and/or no progressive change in cervical dilation or effacement detected by serial examinations, when maternal participant is asymptomatic (i.e. no vaginal bleeding or uterine contractions or amniotic fluid loss).
 - Uncomplicated twin gestation.
- Pregnant females at 24^{0/7} to 36^{0/7} weeks of gestation at the time of study intervention administration (Day 1), as established by:
 - Last menstrual period (LMP) date corroborated by first or second trimester ultrasound examination (U/S) (i.e. at or before 28 weeks of gestation).
 - first or second trimester U/S only, if LMP is unknown/uncertain.
 - Certain LMP, corroborated by an U/S performed after 28 weeks of gestation is also acceptable.

Notes: If pregnancy resulted from assisted reproductive technologies, LMP date may be replaced by intrauterine insemination (IUI) or embryo-transfer (ET) date. Refer to Section 10.8 for guidance on gestational age assessment.

The level of diagnostic certainty of the gestational age should be established by using the GAIA gestation age assessment tool (Section 10.8).

- Participants who are willing to provide cord blood.

- Willing to have their offspring followed-up after delivery for a period of 12 months.
- Participants who do not plan to give their offspring for adoption or place the child in care.

Note that women whose pregnancies resulted from assisted reproductive technologies may be enrolled if they meet all inclusion criteria and none of the exclusion criteria.

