Study intervention Assignment	
Study intervention schedule*: 1 single dose administered IM between 24 and 36 weeks of gestation (at Visit 1, Day 1) to maternal participants.
 
* Due to the recent safety signal, there will be no further enrollment and vaccination of maternal participants.
 
Randomized study intervention allocation* is 2:1 (investigational vaccine: placebo), as described in Table 2.
 
* Due to the recent safety signal, there will be no further enrollment and vaccination of maternal participants.

Conduct of Analyses	
No analysis requiring statistical adjustment will be performed. However, analyses to evaluate objectives and endpoints will be performed in steps. Refer to Section 4.7 for details.

CONFIDENTIAL

Table 2 Study groups, intervention and blinding

Study groups	Maternal participants				Infant participants		Sub-cohorts for randomization (Allocation 1:1:1)	Blinding		
	~Number	Age in years (Min-Max)	Intervention name	Study groups for randomization (Allocation 2:1)	Infant Blood Sampling sub-cohorts			M + I Up to Day 43 post-delivery/birth	M + I Up to Day 181 post-delivery/birth	I only From Day 182 to Day 366 post-delivery/birth
					Name	~Number		Double-blind**	Single-blind**	Single-blind**
RSV_MAT	~252 *	15 – 49	RSV MAT	RSV_MAT	RSV_MAT_BS1	~84	RSV_MAT_BS1	•	•	•
					RSV_MAT_BS2	~84	RSV_MAT_BS2			
					RSV_MAT_BS3	~84	RSV_MAT_BS3			
Control	~126 *	15 – 49	Control	Control	Control_BS1	~42	Control_BS1	•	•	•
					Control_BS2	~42	Control_BS2			
					Control_BS3	~42	Control_BS3			

Control = Placebo; **M** = maternal participants; **I** = infant participants

Infant sub-cohorts are abbreviated “BS1”, “BS2” and “BS3” correspond to Visit 2-NB (Day 43 post-birth), Visit 3-NB (Day 121 post-birth) and Visit 4-NB (Day 181 post-birth), respectively.

RSV_MAT_BS1, _BS2, _BS3 = infants born to women in the RSV_MAT group and evaluated for immunogenicity at the designated timepoint (Day 43, Day 121 or Day 181 post-birth).

Control_BS1, _BS2, _BS3 = infants born to women in the Control group evaluated for immunogenicity at the designated timepoint (Day 43, Day 121 or Day 181 post-birth)

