3.2.3. Elimination from Per-protocol analysis Set (PPS) - Immunogenicity

3.2.3.1. Excluded participants from Per-protocol analysis set of maternal participants

A maternal participant will be excluded from the PPS analysis under the following conditions.

Table 7 Elimination code and condition for maternal participants

Code	Condition under which the code is used	Visit (timepoints) where the code is applicable	Applicable for analysis set/endpoint
800	Fraudulent data	All	All
900	Invalid informed consent	All	All
1030	Study vaccine not administered at all	All	Safety, immunogenicity
1040.Vx+*	Administration of concomitant vaccine(s) forbidden in the protocol	Visit 2/Day 31, Visit 3/Delivery	Immunogenicity
1050	Randomisation failure	All	Immunogenicity
1060	Randomisation code was broken	All	Immunogenicity
1070**	Participants got vaccinated with the correct vaccine but containing an incorrect volume	All	Immunogenicity
1070**	Vaccination not according to protocol (site of injection, route of administration, wrong replacement of study treatment administered)	All	Immunogenicity
1070**	Study treatment not prepared as per protocol (e.g. reconstitution)	All	Immunogenicity
1070**	Other deviations related to wrong study treatment/administration/dose	All	Immunogenicity
1070**	Study treatment administered while contraindication	All	Immunogenicity
1080	Vaccine temperature deviation	All	Immunogenicity
1090	Expired vaccine administered	All	Immunogenicity

CONFIDENTIAL

Code	Condition under which the code is used	Visit (timepoints) where the code is applicable	Applicable for analysis set/endpoint
2010	Protocol violation (inclusion/exclusion criteria) DOB – VAC – 15-49 years Gestational age at vaccination - 28 ^{0/7} - 36 ^{0/7}	All	Immunogenicity
2040.Vx+*	Administration of any medication forbidden by the protocol	Visit 2/Day 31, Visit 3/Delivery	Immunogenicity
2040.Vx+*	Device, excluded by the protocol, was administered	Visit 2/Day 31, Visit 3/Delivery	Immunogenicity
2050.Vx+*	Intercurrent medical conditions which are exclusionary as per protocol	Visit 2/Day 31, Visit 3/Delivery	Immunogenicity
2060.Vx+*	Concomitant infection related to the vaccine which may influence immune response	Visit 2/Day 31, Visit 3/Delivery	Immunogenicity
2070.Vx+*	Concomitant infection not related to the vaccine but may influence immune response	Visit 2/Day 31, Visit 3/Delivery	Immunogenicity

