3.2.3.2. Excluded participants from Per-protocol analysis set of infant participants

An infant participant will be excluded from the PPS analysis under the following conditions.

Table 8 Elimination code and condition for infant participants

Code	Condition under which the code is used	Visit (timepoints) where the code is applicable	Applicable for analysis set/endpoint
800	Fraudulent data	All	All
900	Invalid informed consent - infant	All	All
901#	Invalid informed consent - mother	All	All
1030#	Study vaccine not administered at all	All	Safety, immunogenicity
1040.Vx+*	Administration of concomitant vaccine(s) forbidden in the protocol - infant	Visit 2-NB/Day 43 post-birth Visit3-NB/Day 121 post-birth Visit4-NB/Day 181 post-birth	Immunogenicity
1041#*	Maternal administration of concomitant vaccine(s) forbidden in the protocol up to Delivery	All	Immunogenicity
1050#	Maternal randomisation failure	All	Immunogenicity
1060#	Maternal randomisation code was broken	All	Immunogenicity
1070#	Maternal participants got vaccinated with the correct vaccine but containing an incorrect volume	All	Immunogenicity
1070#	Vaccination not according to protocol (site of injection, route of administration, wrong replacement of study treatment administered)	All	Immunogenicity
1070#	Study treatment not prepared as per protocol (e.g. reconstitution)	All	Immunogenicity
1070#	Other deviations related to wrong study treatment/administration/dose	All	Immunogenicity

CONFIDENTIAL

Code	Condition under which the code is used	Visit (timepoints) where the code is applicable	Applicable for analysis set/endpoint
1070#	Study treatment administered while contraindicated	All	Immunogenicity
1080#	Vaccine temperature deviation	All	Immunogenicity
1090#	Expired vaccine administered	All	Immunogenicity
2010	Protocol violation (inclusion/exclusion criteria) - infant	All	Immunogenicity
2011#	Protocol violation (inclusion/exclusion criteria) - mother	All	Immunogenicity
2040.Vx+*	Administration of any medication forbidden by the protocol - infant	Visit 2-NB/Day 43 post-birth Visit3-NB/Day 121 post-birth Visit4-NB/Day 181 post-birth	Immunogenicity
2040.Vx+*	Device, excluded by the protocol, was administered - infant	Visit 2-NB/Day 43 post-birth Visit3-NB/Day 121 post-birth Visit4-NB/Day 181 post-birth	Immunogenicity
2041#*	Maternal administration of any medication forbidden by the protocol up to Delivery	All	Immunogenicity

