4.3.3. Sensitivity analyses

For primary and secondary immunogenicity endpoints, between study group comparisons will also be explored through statistical modelling. This analysis is exploratory.

For the analysis of maternal participants at each time point (Day 31, Delivery), the ANCOVA model will be explored and fitted via the proc GML procedure according to the following code:

```
PROC GLM data=adis_moth;
  BY atptn atpt;
  CLASS tr01aga gagevg1 agegr3;
  MODEL aval = base tr01aga gagevg1 agegr3 vacdel;
  LSMEANS tr01aga/pdiff cl alpha=0.05;
RUN;
```

where aval represents the log-transformed antibody value of the immunogenicity variable at a given post baseline timepoint, group indicates the study group, gagevg1 is the gestational age category at study intervention administration ($<28^{0/7}$, $\geq 28^{0/7}$ weeks), agegr3 is the age category at study intervention administration (<18 years and ≥ 18 years), vacdel is the interval between vaccination and delivery (days). The inclusion of age category at study intervention administration, interaction term between age category and gestational age category and interval between study intervention administration and delivery in the model depends on the availability of the variables (vacdel may not be available at Day 31 analysis) and the necessity, therefore, the above SAS code serves as a reference and may be adjusted according to the analysis needs. Other possible co-variables which could be included in the model, but not limited to, are pre-existing HIV infection status, CD4 count, COVID-related complications.

For the analysis of infants at each time point (cord blood at Delivery, Day 43 post-birth, Day 121 post-birth, and Day 181 post-birth), similar model will be explored:

```
PROC GLM data=adis;
  BY atptn atpt;
  CLASS tr01aga gagevg1 gagebg1 agegr3;
  MODEL aval = base tr01aga gagevg1 gagebg1 agegr3;
  LSMEANS tr01aga/pdiff cl alpha=0.05;
RUN;
```

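### The SAP's per-protocol eligibility check starts at 28 weeks' gestation, although women are eligible from 24 weeks, so eligible women and their infants would drop out of the primary immunogenicity set

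*SAP*

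**What the plan says.** **Eligibility.** Protocol 5.1.1 admits "Pregnant females at 24^{0/7} to 36^{0/7} weeks of gestation at the time of study intervention administration (Day 1"). Protocol 1.2 and 4.3 give the same range, and SAP 1.2 describes "1 single dose administered IM between 24 and 36 weeks of gestation (at Visit 1, Day 1) to maternal participants".

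**The check.** SAP Table 7 lists the reasons for removing a mother from the PPS. Code 2010 is headed as a violation of the inclusion or exclusion criteria and names two checks. The age check, 15–49 years, agrees with the protocol. The other begins "Gestational age at vaccination - 28" 0/7 weeks, with an upper limit of 36 0/7. The code applies at all visits. It carries neither the single asterisk (review of an individual listing) nor the double asterisk (confirmation) that Table 7 attaches to some other codes.

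**Infants.** SAP Table 8 contains code 2011, "Protocol violation (inclusion/exclusion criteria) - mother", also at all visits. Its # mark means that the mother's elimination is carried forward to the infant.

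**Use of the set.** SAP 4.2.2.1 makes the PPS the primary set for immunogenicity. Under SAP 4.1, a second analysis on the full analysis set (FAS) complements it when 5% or more are excluded in any group at any timepoint.

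**The concern.** A check on entry criteria should flag only women who broke them. A woman dosed at 25 weeks broke none, yet the printed range makes her a violator.

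The rest of the plan expects such women in the PPS. Gestational age at dosing, below 28 0/7 against 28 0/7 or later, is a minimisation factor (Protocol 6.3.3) and a listed covariate in the between-group models (SAP 4.2.2.1 and 4.3.2.1). It appears in the sample code of SAP 4.3.3, where "gagevg1 is the gestational age category at study intervention administration", and SAP 6.1.2.1 summarises the same split on the PPS. With the 28-week limit the lower category is empty in that set.

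At stake is the population that the primary immunogenicity results describe. For any given gestational age at delivery, women dosed before 28 weeks have had the longest interval between dosing and delivery. Their antibody levels and placental transfer are part of what the trial set out to measure.

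**Working it through.** **1. Text comparison**

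| Place | Gestational age at dosing |
|---|---|
| Protocol 1.2, 4.3, 5.1.1 | 24 0/7 to 36 0/7 weeks |
| SAP 1.2 | 24 to 36 weeks |
| SAP Table 7, code 2010 | 28 0/7 to 36 0/7 weeks |
| Minimisation factor, model covariate, PPS baseline table | below 28 0/7; 28 0/7 or later |

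SAP 4.8, which lists departures from the protocol's analyses, mentions only the dropped distribution analyses and scatter plots. Protocol 9.3.1.2 permits elimination for violations linked to the entry criteria, and dosing at 24 0/7 to 27 6/7 weeks is not one. No text supports a deliberate restriction.

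**2. The plan's own precision**

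Inputs from SAP 5 and 5.2: 252 vaccinees, 10% non-evaluable, log10 SD 0.4.

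- Evaluable vaccinees: 252 × 0.9 = 226.8, stated as 226. All women: 378 × 0.9 = 340.2, stated as 340.
- Half-width = t(0.975, n−1) × SD × √2 / √n. At n = 226 and SD 0.4 this is 0.0742; at SD 0.3 it is 0.0556. SAP Table 14 prints 0.074 and 0.056. The √2 (no correlation between the pre-dose and delivery values) is inferred: without it the result at SD 0.4 is 0.0524, which does not match.
- Interval = 10^(log10 fold ± half-width). For 9-fold: 7.59 to 10.68, printed as 7.6 to 10.7.

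**3. Share of the window excluded**

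- 24 0/7 to 36 0/7 inclusive is 12 × 7 + 1 = 85 days.
- 24 0/7 to 27 6/7 is 4 × 7 = 28 days.
- 28/85 = 0.329, the share if dosing were spread evenly. The true share is not in the documents, so a range is shown.

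**4. Effect on the vaccine group of the PPS** (remaining n = 226 × (1 − share), rounded down; SD 0.4)

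| Assumed share dosed before 28 0/7 | Lost | Remaining | Half-width | 95% CI for 9-fold |
|---|---|---|---|---|
| 0% | 0 | 226 | 0.074 | 7.6–10.7 |
| 5% | 12 | 214 | 0.076 | 7.6–10.7 |
| 10% | 23 | 203 | 0.078 | 7.5–10.8 |
| 20% | 46 | 180 | 0.083 | 7.4–10.9 |
| 33% (28/85) | 75 | 151 | 0.091 | 7.3–11.1 |
| 50% | 113 | 113 | 0.105 | 7.1–11.5 |

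At every share above zero, the PPS contains no woman dosed before 28 weeks and, through code 2011, no infant of such a woman.

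**The case against.** The strongest reply is that this is a transcription slip that would not be carried out. The code's heading refers to protocol violations, the PPS removes only participants with deviations that lead to exclusion, and the neighbouring age check is correct. A programmer might well apply 24 weeks, and SAP 6.1.3 plans a review of deviations leading to exclusion before the database is frozen. The slip is plausible, so the loss is what follows if the printed range is used, not something known to have happened. But the SAP is what programmers work from, code 2010 carries no mark for individual review, and a silent departure from the table would itself be undocumented.

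The FAS does offer protection. It does not use code 2010, and if the check removes 5% or more in any group the FAS analysis must be run. The affected women and infants would then be reported, but only in a complementary analysis. The safety sets are untouched.

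The point about the models needs limits. The covariates are to be included if needed, and the SAP says its code may be adjusted. A constant covariate contributes nothing, but the treatment contrast can still be estimated. Gestational age at dosing is not one of the planned subgroups in SAP 4.6.2, so no planned subgroup estimate is lost.

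Finally, the study is descriptive, enrolment stopped early (Protocol 2.3) and the actual numbers are not given. The table therefore shows scale only.

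**Conclusion.** The concern holds. The lower limit in SAP Table 7, code 2010, contradicts the protocol's entry criterion and the SAP's own design section. Followed literally, it takes all eligible women dosed at 24 0/7 to 27 6/7 weeks, and their infants, out of the primary immunogenicity analyses. That conclusion rests on comparing the texts and on no statistical assumption.

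The loss of precision is moderate: over assumed shares of 10% to 33%, the half-width rises from 0.074 to between 0.078 and 0.091. Those figures assume the planned 226 evaluable vaccinees, SD 0.4 and an unknown share dosed early. The more serious effect is that the primary set no longer represents the population the trial enrolled. It must be corrected before the analysis sets are finalised.

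**What to change.** In SAP Table 7, code 2010, change the lower limit of the gestational-age check from 28 0/7 to 24 0/7, so that it matches Protocol 5.1.1 and SAP 1.2. Make the same change in any programming specification built from the table, and derive infant code 2011 from the corrected maternal flag. If a narrower per-protocol population was in fact intended, SAP 4.8 must declare and justify it, and the covariate and baseline split at 28 weeks must be revised.

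The cost is one number in the SAP. The correction aligns an analysis-set check with the stated eligibility range; it alters no clinical rule, and with it the planned 226 and 340 evaluable women lose none to this check.

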3.2.3.2. Excluded participants from Per-protocol analysis set of infant participants

An infant participant will be excluded from the PPS analysis under the following conditions.

Table 8 Elimination code and condition for infant participants

Code	Condition under which the code is used	Visit (timepoints) where the code is applicable	Applicable for analysis set/endpoint
800	Fraudulent data	All	All
900	Invalid informed consent - infant	All	All
901#	Invalid informed consent - mother	All	All
1030#	Study vaccine not administered at all	All	Safety, immunogenicity
1040.Vx+*	Administration of concomitant vaccine(s) forbidden in the protocol - infant	Visit 2-NB/Day 43 post-birth Visit3-NB/Day 121 post-birth Visit4-NB/Day 181 post-birth	Immunogenicity
1041#*	Maternal administration of concomitant vaccine(s) forbidden in the protocol up to Delivery	All	Immunogenicity
1050#	Maternal randomisation failure	All	Immunogenicity
1060#	Maternal randomisation code was broken	All	Immunogenicity
1070#	Maternal participants got vaccinated with the correct vaccine but containing an incorrect volume	All	Immunogenicity
1070#	Vaccination not according to protocol (site of injection, route of administration, wrong replacement of study treatment administered)	All	Immunogenicity
1070#	Study treatment not prepared as per protocol (e.g. reconstitution)	All	Immunogenicity
1070#	Other deviations related to wrong study treatment/administration/dose	All	Immunogenicity

CONFIDENTIAL

Code	Condition under which the code is used	Visit (timepoints) where the code is applicable	Applicable for analysis set/endpoint
1070#	Study treatment administered while contraindicated	All	Immunogenicity
1080#	Vaccine temperature deviation	All	Immunogenicity
1090#	Expired vaccine administered	All	Immunogenicity
2010	Protocol violation (inclusion/exclusion criteria) - infant	All	Immunogenicity
2011#	Protocol violation (inclusion/exclusion criteria) - mother	All	Immunogenicity
2040.Vx+*	Administration of any medication forbidden by the protocol - infant	Visit 2-NB/Day 43 post-birth Visit3-NB/Day 121 post-birth Visit4-NB/Day 181 post-birth	Immunogenicity
2040.Vx+*	Device, excluded by the protocol, was administered - infant	Visit 2-NB/Day 43 post-birth Visit3-NB/Day 121 post-birth Visit4-NB/Day 181 post-birth	Immunogenicity
2041#*	Maternal administration of any medication forbidden by the protocol up to Delivery	All	Immunogenicity
2041#*	Device, excluded by the protocol, was administered by mother up to Delivery	All	Immunogenicity
2050.Vx+*	Intercurrent medical conditions which are exclusionary as per protocol - infant	Visit 2-NB/Day 43 post-birth Visit3-NB/Day 121 post-birth Visit4-NB/Day 181 post-birth	Immunogenicity
2060.Vx+*	Concomitant infection related to the vaccine which may influence immune response - infant	Visit 2-NB/Day 43 post-birth Visit3-NB/Day 121 post-birth Visit4-NB/Day 181 post-birth	Immunogenicity

CONFIDENTIAL

Code	Condition under which the code is used	Visit (timepoints) where the code is applicable	Applicable for analysis set/endpoint
2070.Vx+*	Concomitant infection not related to the vaccine but may influence immune response - infant	Visit 2-NB/Day 43 post-birth Visit3-NB/Day 121 post-birth Visit4-NB/Day 181 post-birth	Immunogenicity
2050#*	Maternal intercurrent medical conditions which are exclusionary as per protocol up to Delivery	All	Immunogenicity
2060#*	Maternal concomitant infection related to the vaccine which may influence immune response up to Delivery	All	Immunogenicity
2070#*	Maternal concomitant infection not related to the vaccine but may influence immune response up to Delivery	All	Immunogenicity
2090.Vx	
Participants did not comply with blood sample schedule – infant:
 
 • For infants without cord blood, check the interval from birth to Visit 1-NB birth BS = 0 – 72 hours; • For PPS at Day 43 post-birth, check the interval from birth to Day 43 BS = 30 – 60 days; • For PPS at Day 121 post-birth, check the interval from birth to Day 121 BS = 110 – 140 days; • For PPS at Day 181 post-birth, check the interval from birth to Day 181 BS = 165 - 200 days 	Visit 1-NB/Birth Visit 2-NB/Day 43 post-birth Visit3-NB/Day 121 post-birth Visit4-NB/Day 181 post-birth	Immunogenicity

CONFIDENTIAL

Code	Condition under which the code is used	Visit (timepoints) where the code is applicable	Applicable for analysis set/endpoint
2100.Vx	Serological results not available	Visit 1-NB/Birth Visit 2-NB/Day 43 post-birth Visit3-NB/Day 121 post-birth Visit4-NB/Day 181 post-birth	Immunogenicity
2120.Vx	Obvious incoherence or abnormality or error in data	Visit 1-NB/Birth Visit 2-NB/Day 43 post-birth Visit3-NB/Day 121 post-birth Visit4-NB/Day 181 post-birth	Immunogenicity
2130.Vx	Testing performed on samples not aligned with ICF	Visit 1-NB/Birth Visit 2-NB/Day 43 post-birth Visit3-NB/Day 121 post-birth Visit4-NB/Day 181 post-birth	Immunogenicity
3100	Delivery happens less than 4 weeks post vaccination	All	Immunogenicity

*Attribution of these elimination codes to subject need CRDL review of individual listing

#Carry forward elimination from mother to infant

Vx+ indicates subjects whose immunogenicity data will be eliminated from a specific visit onwards; Vx indicates subjects whose immunogenicity data will be eliminated from a specific visit.

BS- Blood Sample.

